16.3.1 Primary Efficacy Endpoints and Statistical Model of Analysis

The primary endpoint is the change in weekly global gastrointestinal symptoms average index score from pre-treatment to the end of each treatment period.

The average weekly global gastrointestinal symptoms index score is obtained by averaging the scores for each of the 4 symptoms assessed weekly: abdominal pain, bloating, nausea and vomiting. The use of the average of the 4 symptom scores to obtain a global score is similar to the scoring methodology applied for largely used patient questionnaires such as PAGI-SYM (Patient Assessment Gastrointestinal Symptoms) and ANMS-GCSI-DD (American Neurogastroenterology and Motility Society – Gastroparesis Cardinal Symptom Index – Daily Diary).

Rating of symptoms (i.e. abdominal pain, bloating, nausea, vomiting) is using a recall period of 7 days and a Likert scale with the following categories:

- 0 Absent
- 1 Mild (not influencing usual activities)
- 2 Moderate (diverting from, but not urging modification of, usual activities)
- 3 Severe (influencing usual activities markedly enough to urge modifications)
- 4 Extremely severe (precluding daily activities)

The average s	score	ranges	thus	between	0	and 4	- with	lower	scores	representing	a	better	health	for
the subject.														

The primary analysis is performed on the mFAS1.

A stratified t-test will be used to analyze the treatment effect. For the primary analysis on the mFAS1, missing pairs will not be imputed (each subject contributing to at least one pair).

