In case, during a treatment period or during a washout period, a subject should experience an exacerbation of the CIPO related gastrointestinal symptoms that is not controlled by permitted medications and is not judged as an adverse event, he/she will attend an early switch visit (ESV) at the clinical site. After being reassessed, he/she will be offered to directly switch to the next scheduled treatment period (SOT-2 or SOT-3 or SOT-4) without completing the ongoing treatment or washout period. Only one early switch is possible during the study. ESV will be Day 1 of the relevant period (SOT-2 or SOT-3) based on the timing of early switch.

In case of ESV/SOT-2 or ESV/SOT-3 or ESV/SOT-4, the subsequent visits will follow the relevant sequential number (see Study Schedule of Assessments).

will be registered on Day-1 (taking into consideration the symptoms relevant to the last 7 days including Day-1) and weekly after randomization, during both treatment and wash out periods, as appropriate according to the Study Schedule of Assessments using a subject's e-diary, until End of Follow-up or in case of ETV or ESV.

[figure not shown]
In addition, investigational product intake and time will be registered by the subjects in the e-diary during the treatment periods daily.

will be also assessed at screening and then, after randomization during the study according to "Study Schedule of Assessments".

At the screening visit and at the end of the first 4-week treatment period, will be performed in order to assess

In order to assess in all subjects on Visit 2 (Day 1) and Visit 3 (Day 28 ± 1), blood samples for assessment of plasma velusetrag and THRX 830449 (metabolite) concentrations will be collected.

Figure 1: Schematic study design

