11.2.8 Early Switch Visit (ESV; anytime between Day 1 and Day 126)

The following procedures/assessments will be completed in case of ESV occurrence (see section 6 Overall Study Design and Plan): The ESV will be considered as Day 1 of SOT-2 or SOT-4, as appropriate.

Pre-dose

- 1. 2. 3. 4. 5.
- Blood collection (in fasting condition):

- 13. Review and record any AEs that occurred since the previous visit.
- 14. Review the e-diary to assess the completeness and retrain the subject as needed. Weekly questionnaire will be completed during this visit. Questionnaires not yet completed should be completed by the subject at the clinical center before investigational product administration
- 15.
- 16. Collect all investigational product bottles and account investigational product (if applicable).
- 17. Dispense investigational product.

Dosing:

Investigational product dose will be administered under the supervision of the study personnel, in the morning, on an empty stomach, with water. Time of dosing will be registered. After the investigational product administration, the following procedures will be completed:

Post-dose:

- 18.
- 19. Schedule next visit and remind the subject not to take the investigational product in the morning of the next visit, but to bring the bottle to the clinic, if the visit is scheduled at the clinical center; If the subject cannot go back to the clinical center for the next visit (EOT), a home visit will be scheduled for the subject.

After this visit, the subsequent visits will follow the relevant sequential number (see Study Schedule of Assessments).

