16 STATISTICAL PLAN AND DETERMINATION OF SAMPLE SIZE

16.1 DETERMINATION OF SAMPLE SIZE

The sample size is based on the main analysis (t-test) of the primary endpoint that consists of the differences between velusetrag and placebo within each paired treatment cycle (2 per subject).

A total of 16 subject randomized leading to 32 pairs. Accounting for 25% dropouts/missing pairs, 18 pairs should be available for the primary analysis on the subgroup of subjects with history of benefit from , and 24 pairs should be available for the or naïve to analysis on the overall population

With a two-sided significance level of 5%, the planned sample size will lead to power levels above 80% to detect effect size (ES) above 0.7 (see table 16.1 below).

Power for different values of effect size and number of pairs **Table 16.1**

Power for different values of Effect Size* and number of pairs								
Number of pairs ES: 0.6 ES: 0.7 ES: 0.8								
18	67%	80%	89%					
24	80%	91%	96%					
28	86%	94%	98%					
32	91%	97%	99%					

^{*} More than medium to moderate effect size (Cohen, 1988)

Estimates obtained using SAS PROC POWER

If based on a blinded review of the data, the rate of missing pairs is found to be higher the sample size might be increased by the Sponsor.

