16.3.5 Handling of Missing and Incomplete Data

Primary endpoint

Missing pairs (treatment difference velusetrag minus placebo) can occur when at least one of the following is missing:

- Pre-treatment velusetrag value missing
- End of treatment velusetrag value missing
- Pre-treatment placebo value missing
- End of treatment placebo value missing

If the pre-treatment value is missing for a period, the average of the values of other subjects starting this period will be used.

If, within a period, intermediate values (from pre-treatment value up to the end of a period) are available, the last observation carried forward will be used to impute the end of treatment value. ESV will be considered as SOT-2 or SOT-3 or SOT-4, as appropriate.

The above approach will be used for the FAS and as sensitivity analysis for mFAS1, PPS

Other endpoints:

Missing continuous efficacy endpoints will be using the same approach as the primary endpoint.

For binary outcomes, missing data will be considered as failures.

Details will be provided in the SAP.

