For efficacy evaluation after the discontinuation of each treatment, the reference for changes computation is defined as the end of treatment visit for each period: Visit 3 (EOT-1) for period 1, Visit 5 (EOT-2) for period 2, Visit 7 (EOT-3) for period 3 and Visit 9 (EOT-4) for period 4.

| | |
|---|--|
|  | Statistical Analysis Plan |
| | Sponsor: Alfasigma S.p.A. Protocol: VE-CIP2001/2021 |

In case of early switch visit or premature interruption of treatment, the reference for changes computation within each period should be adjusted accordingly based on ESV visits.

First/Last Administration of Study Treatment

Considering the overall study, the date of first administration of treatment (i.e., velusetrag or placebo) is the earliest start date of the 4 periods reported in the “Study treatment dispensed” CRF page while the date of last administration of treatment (i.e., velusetrag or placebo) is the date reported in the “End of treatment disposition” CRF page (i.e., maximum of the last administration of the 4 periods).

According to the study design, subjects will not receive the treatment during the wash out periods. For each study period, the date of first administration of treatment is the start date reported in the “Study treatment dispensed” CRF page on the corresponding SOT visit (i.e., Visit 2 (SOT-1) for period 1, Visit 4 (SOT-2) for period 2, Visit 6 (SOT-3) for period 3 and Visit 8 (SOT-4) for period 4) while the date of last administration of treatment is the last treatment intake date reported in the “Study treatment returned” CRF page on the corresponding EOT visit (i.e., Visit 3 (EOT-1) for period 1, Visit 5 (EOT-2) for period 2, Visit 7 (EOT-3) for period 3 and Visit 9 (EOT-4) for period 4). In case of early switch visit or premature interruption of treatment, the first and last intake within each period should be adjusted accordingly.

Study day

The study day describes the day of the event or assessment date relative to the reference start date, which is defined as the date of Randomization.

The study day will be calculated as the difference between the date of each considered efficacy/safety assessment and the reference start date plus 1 day.

If the considered event starts before the Randomization date, the study day will be calculated as the difference between the date of the assessment and the reference start date. Therefore, the study day will be negative.

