6.3. Efficacy Evaluation

6.3.1. Primary efficacy analysis

Definition of primary endpoint

The primary endpoint is the change in weekly global gastrointestinal symptoms average index score from pre-treatment (Baseline/Reference, depending on the period) to the end of each treatment period.

The weekly global gastrointestinal symptoms average index score is obtained by averaging the scores for each of the 4 symptoms assessed weekly: abdominal pain, bloating, nausea and vomiting.

Each symptom (i.e., abdominal pain, bloating, nausea, vomiting) was rated using a recall period of 7 days and a Likert scale with the following categories:

- 0 – Absent
- 1 - Mild (not influencing usual activities)
- 2 - Moderate (diverting from, but not urging modification of, usual activities)
- 3 - Severe (influencing usual activities markedly enough to urge modifications)
- 4 - Extremely severe (precluding daily activities)

[figure not shown]
[figure not shown]
[figure not shown]

Analysis methodology

| | |
|---|--|
|  | Statistical Analysis Plan |
| | Sponsor: Alfasigma S.p.A. Protocol: VE-CIP2001/2021 |

Considering the evaluable pairs  the  will be summarized 

Of note, each subject should be evaluated twice: once for each cycle. Consequently, each subject can contribute to 0, 1 or 2 pairs and only data that constitute pair evaluable for primary endpoint will be considered in this and in the following analysis.

Differences between velusetrag and placebo will be computed within each cycle 

These analyses will be provided on the mFAS1 without any missing data imputation as primary analysis.

Finally, a listing will be provided on Randomized population considering the intake of each  collected in the eDiary together with the individual gastrointestinal symptoms and the weekly global gastrointestinal symptoms average index score.

Data handling rules

Missing data will be handled as described in [Section 4.4.2](#).

[figure not shown]
Sensitivity analysis

| | |
|---|--|
|  | Statistical Analysis Plan |
| | Sponsor: Alfasigma S.p.A. Protocol: VE-CIP2001/2021 |

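### The protocol's primary t-test uses raw change from a separate one-week baseline in each period, with no baseline covariate; this usually wastes precision and lets an exacerbation score from an early switch become the baseline

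*Protocol*

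**What the plan says.** Protocol 16.3.1 defines the endpoint: "The primary endpoint is the change in weekly global gastrointestinal symptoms average index score from pre-treatment to the end of each treatment period". The analysis follows: "A stratified t-test will be used to analyze the treatment effect". Protocol 16.1 fixes the unit as the velusetrag-placebo difference within a cycle, two cycles per subject, and says "The sample size is based on the main analysis (t-test) of the primary endpoint". Neither section names a baseline covariate. SAP 3.5 repeats the t-test as the main analysis, and SAP 1.1 drops the stratification.

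Each baseline is one e-diary questionnaire with 7-day recall: Day -1 for Period 1 and the end of washout for Periods 2 to 4 (SAP 4.2).

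On the early switch visit (ESV):
- Its trigger is an "exacerbation of the CIPO related gastrointestinal symptoms that is not controlled by permitted medications" (Protocol 6).
- "Weekly questionnaire will be completed during this visit" (Protocol 11.2.8, among the pre-dose steps).
- "ESV will be considered as SOT-2 or SOT-3 or SOT-4, as appropriate" (Protocol 16.3.5).
- After an early switch, "the reference for changes computation within each period should be adjusted accordingly based on ESV visits" (SAP 4.2).

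SAP 6.3.1 says "Differences between velusetrag and placebo will be computed within each cycle". The text after that, including the sensitivity analysis, is redacted. The SAP version log mentions mixed models for continuous efficacy parameters.

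**The concern.** There are two issues, both arising from the use of raw change.

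**Precision.** The within-cycle difference already cancels the subject's own symptom level, which is the usual reason for taking change from baseline. What the two baselines then bring in is mostly week-to-week fluctuation, and Protocol 7 itself describes CIPO symptoms as fluctuating. With only 18 pairs expected for the primary analysis, the lost precision matters.

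**Early switch.** A score recorded because symptoms flared is likely to fall afterwards whatever is given. If it serves as the next period's baseline, that fall is counted as a response to the next treatment. Should switches be more frequent after one treatment than after the other, the raw-change estimate is biased; if they are equally frequent, it only becomes noisier.

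**Working it through.** **1. The plan's own figure.** Paired t-test, n pairs, two-sided 5%, n-1 degrees of freedom, noncentrality ES × √n. At 18 pairs this gives 67.0%, 79.9% and 89.2% for ES 0.6, 0.7 and 0.8 (stated: 67, 80, 89%). At 24 pairs and ES 0.6 it gives 80.4% (stated: 80%). The power table is correct.

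**2. Variance of one pair.** Let s² be the within-subject variance of a weekly score, taken as equal at baseline and end of period, and r the within-subject correlation between a period's baseline and its end score about 4 weeks later. Treat periods as independent once the subject's level is removed.
- Raw change: 2 × 2s²(1-r) = 4s²(1-r).
- End-score difference, adjusted for the baseline difference: 2s²(1-r²).
- Ratio: 4s²(1-r) / [2s²(1-r²)] = 2/(1+r), that is 2.00 at r = 0, 1.54 at r = 0.3 and 1.18 at r = 0.7.

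**3. Power with the covariate.** The true effect is held at the stated ES on the change scale. There were 40,000 simulated trials per cell, and the adjusted test has n-2 degrees of freedom.

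| r (assumed) | 0 | 0.1 | 0.3 | 0.5 | 0.7 | 0.8 | 0.9 |
|---|---|---|---|---|---|---|---|
| 18 pairs, ES 0.7 (raw 80%) | 97% | 95% | 92% | 88% | 84% | 81% | 79% |
| 24 pairs, ES 0.6 (raw 80%) | 97% | 96% | 92% | 89% | 85% | 83% | 80% |

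Type I error is 4.7-5.1% for both tests. At 18 pairs, the cost of estimating the slope cancels the gain at about r = 0.87.

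**4. Direction of the early-switch effect.** Sequences A to D contain 12 between-period washouts. Of the 6 after velusetrag, 5 lead into placebo (the exception is sequence D after Period 2). Of the 6 after placebo, 5 lead into velusetrag (the exception is sequence C after Period 2). Switches after velusetrag therefore mostly raise placebo baselines and work against velusetrag; switches after placebo mostly work in its favour.

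**5. Size of the early-switch effect.** One baseline raised by 1 point moves its pair by 1 point and the mean of 18 pairs by 1/18 = 0.056. The simulation used 12 subjects (3 per sequence), 18 of 24 pairs kept at random, s = 0.6, an ESV score 1 point above usual, at most one switch per subject, and 4,000 runs per cell. All these values except the 18 pairs and the one-switch limit are assumptions. The true effect is 0.7 × √[4 × 0.36 × (1-r)]: 0.70 at r = 0.3 and 0.46 at r = 0.7, as a reduction. Entries are the mean estimate, with power in brackets.

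| Washouts ending in a switch | r = 0.3, raw | r = 0.3, adjusted | r = 0.7, raw | r = 0.7, adjusted |
|---|---|---|---|---|
| 20%, after velusetrag only | -0.61 (63%) | -0.68 (89%) | -0.38 (52%) | -0.41 (69%) |
| 20%, after both | -0.70 (72%) | -0.70 (92%) | -0.46 (61%) | -0.46 (75%) |
| 20%, after placebo only | -0.80 (85%) | -0.73 (94%) | -0.55 (84%) | -0.51 (86%) |

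- With no switches at r = 0.3, power is 81% raw and 92% adjusted. So 11 of the 26 points between 63% and 89% are the precision effect of step 3.
- At a 10% one-sided rate and r = 0.3, the raw estimates are -0.66 (after velusetrag) and -0.75 (after placebo).
- The covariate leaves about a quarter of the bias at r = 0.3 and somewhat over half at r = 0.7.
- Leaving out pairs with an ESV baseline (on average 2.5 of 18 at a one-sided 20% rate) brings the estimate within 0.01 of the truth.
- With no drug effect, rejection is at most 7.6% raw and 6.8% adjusted.

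**6. Switches during treatment.** These were not simulated. In Period 1 or 3 the pair is lost if the period has no end value, because the primary analysis does not impute missing pairs. If the ESV score were also used as the end value of the shortened period, a score d points too high would move the pair by 2d. A switch during Period 2 makes the ESV the start of Period 3, where the second cycle can remain evaluable.

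**The case against.** **The SAP analysis cannot be seen.** A baseline term and an ESV sensitivity analysis would both sit in redacted parts of SAP 6.3.1, and the version log mentions mixed models. This stands: the point cannot be extended to the SAP, and the first request has to be for confirmation. It does not change what the protocol specifies.

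**The first part is a preference about efficiency.** True in that the unadjusted test is valid and the gain depends on an unknown r: 17 points at r = 0, about 4 at r = 0.7, and minus 1 at r = 0.9. The formula also assumes equal baseline and end variances, which is doubtful in Period 1, where entry requires two symptoms scored 3 or more. But the covariate is already collected and costs one degree of freedom.

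**Eighteen pairs may be too few.** SAP 1.1 reports that all subjects but one fell in Stratum 2. If 16 were randomized and the one exception is a non-responder (the label is redacted), 15 × 2 × 0.75 = 22.5 pairs are expected. Power at ES 0.7 is then 88-89% raw, against 94-95% (r = 0.5) or 91-92% (r = 0.7) adjusted. The gain shrinks but remains.

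**The ESV score as baseline is an inference.** The sentence in Protocol 16.3.5 belongs to the imputation rules. The one in SAP 4.2 follows a paragraph on changes after treatment stops, and SAP 4.2 elsewhere places the e-diary reference on the day before the start-of-treatment visit. Against this, the questionnaire is completed pre-dose at the ESV, that visit is Day 1 of the next period, and Protocol 16.2.5 takes the last value before treatment as baseline. The inference is reasonable, and the ambiguity itself needs resolving.

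**The switch rates are stylised.** They are. A 20% rate after both treatments means 1 - 0.8³ = 49% of subjects switching in a washout, and the one-sided cases assume no switches at all after the other treatment. The figures show sensitivity and are not forecasts.

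**Conclusion.** The point holds for the protocol. The primary t-test is valid and its power table is right, but raw change gives up precision that a score already collected would recover unless r exceeds about 0.87. At 18 pairs and ES 0.7 the unused power is about 12 points at r = 0.3 and 4 at r = 0.7, and somewhat less if 22 or 23 pairs are available.

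The early-switch effect is bias only when switches are unbalanced between the preceding treatments. At an assumed one-sided 20% rate it moves the estimate by roughly 0.1 point on the 0-4 scale, in a direction set by the treatment before the switch. The covariate reduces this but does not remove it. Confidence is medium, because r, the switch rate and the size of the exacerbation are all assumed and the SAP model cannot be read.

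**What to change.** Keep the endpoint data and the cycle pairs. Before unblinding:

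1. Confirm that the SAP primary model already contains the period baseline. If it does not, analyse the within-cycle difference in end-of-treatment score with the within-cycle difference in pre-treatment score as covariate, or use the equivalent mixed model with period baseline.
2. State which score is the reference for a period that starts at an ESV, and whether the ESV score also serves as the end value of a shortened period.
3. Unless the redacted text already has one, add a sensitivity analysis that leaves out pairs whose baseline is an ESV score. Report the number of such pairs by preceding treatment. This analysis uses fewer pairs, so it should support the primary analysis and not replace it.

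The cost is SAP wording and one degree of freedom. No new data are needed.

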16.3.2 Secondary Efficacy Endpoints and Statistical Model of Analysis

Continuous efficacy endpoints will be summarized and analyzed in the same way as the primary endpoint. In case of deviation from normality, non-parametric method will be considered. Binary outcome will be compared between treatments with an odds ratio and confidence interval using logistic model and Cochran-Mantel-Haenszel test. Poisson modelling will be used for count data. Full details will be provided in the SAP.

16.3.4 Statistical Analysis of Adverse Events

Adverse events starting on or after the first intake of investigational product are considered treatment emergent AEs (TEAEs). Verbatim terms for AEs will be coded using the most current version of MedDRA coding.

An overview of the number and percentage of subjects with at least one TEAEs listed above will also be produced.

In addition, events will be classified as velusetrag emergent if the last treatment taken before the start of the adverse event was velusetrag, or placebo emergent if the last treatment taken before the start of the adverse event was placebo. All summaries described above will be done according to this classification.

16.3.5 Handling of Missing and Incomplete Data

Primary endpoint

Missing pairs (treatment difference velusetrag minus placebo) can occur when at least one of the following is missing:

- Pre-treatment velusetrag value missing
- End of treatment velusetrag value missing
- Pre-treatment placebo value missing
- End of treatment placebo value missing

If the pre-treatment value is missing for a period, the average of the values of other subjects starting this period will be used.

If, within a period, intermediate values (from pre-treatment value up to the end of a period) are available, the last observation carried forward will be used to impute the end of treatment value. ESV will be considered as SOT-2 or SOT-3 or SOT-4, as appropriate.

The above approach will be used for the FAS and as sensitivity analysis for mFAS1, PPS

Other endpoints:

Missing continuous efficacy endpoints will be using the same approach as the primary endpoint.

For binary outcomes, missing data will be considered as failures.

Details will be provided in the SAP.

